# 4.3 Assessment and Management of Risk

There is minimal risk to a participant by participating in this study as the assessments taking place are routine and generally non-invasive. The schedule of assessments in this study are designed to evaluate for longer term durability and safety associated with the subretinal administration of the antecedent gene therapy.

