#### 5.9.3.2 Statistical Methods - Secondary Outcome Analysis

The secondary outcomes are measures of the efficacy of each ATIMP; these will be performed on an individual participant basis and will be primarily descriptive in nature. Standard assessments will be used to measure visual function and established methods of analysis, appropriate for the assessment will be used to evaluate the data. For specialist assessments, data will be analysed by the expert team member(s) who developed the assessment. Final data will be reported descriptively.

Efficacy will be indicated by:

- 1) Any improvement in visual function from baseline that is greater that the test-retest variation for that test and is sustained for at least 2 consecutive assessments.
- 2) Any improvement in retinal function from baseline that is greater than test-retest variation and measurable by electrophysiology (pattern ERG, or full-field ERG).

Measures will be reported individually and aggregated across participants as the proportion who satisfy the above criteria.

Quality of life patient reported outcome measures will be used to correlate a participant's feeling about their own wellbeing with clinical observations.

Any deviations from the original statistical plan will be described in the final report, as appropriate.

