2.1.2 Secondary Objective

The secondary research objective is to explore the longer-term efficacy of AAV8-hCARp.hCNGB3 and AAV8-hG1.7p.coCNGA3 in improving visual and retinal function, and quality of life.

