3.5 Efficacy Evaluation

3.5.1 Test-Retest

The test-retest values from studies MGT006 and MGT012 will be used for the MGT007 final analyses.

The protocol describes efficacy as being indicated by:

Any improvement in visual function from baseline that is greater than the test-retest variation for that test and is sustained for at least 2 consecutive assessments.

Participants who have a post baseline reading greater than the test-retest value for at least 2 consecutive assessments will be classed as a visual function improvement for the relevant test.

The test-retest variation for each visual function assessment will be calculated for each participant who has at least one set of test-retest data as:

$$Test - retest = 1.96 \sqrt{S_p^2}$$

where S_p^2 is the within-participant variance for each participant and will be derived as:

$$\frac{(n1-1)\sum_{(yi1-ybar1)}2+(n2-1)\sum_{(yi2-ybar2)}2}{n1+n2-g}$$

Where:

yi1 is the ith baseline observation in the left eye
ybar1 is the mean of baseline observations in the left eye
yi2 is the ith baseline observation in the right eye
ybar2 is the mean of baseline observations in the right eye
n1= number of baseline observations in the left eye
n2= number of baseline observations in the right eye
g is the number of eyes =2

The test-retest variation for each visual function assessment of the difference between the study eye and fellow eye will also be calculated for each participant who has at least one set of test-retest data using the same formula except S_n^2 will be derived as

$$\frac{\sum_{(yi-ybar)}2}{n-g}$$

Where:

yi is the ith baseline observation in the difference of the study eye and fellow eye ybar is the mean of baseline observations in the difference of the study eye and fellow eye n= number of baseline observations in the difference of the study eye and fellow eye (vary from 2 to 3) g is 1

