3.5.2 Visual Acuity

Visual acuity was assessed at the Month 9, 12, 18, 24, 36, 48, and 60 visits.

4 meter refraction of the sphere, cylinder, and axis of each eye will be measured. Best-corrected ETDRS visual acuity will be measured.

The arithmetic mean of the multiple observations at baseline will be used as the baseline value.

Achievement of visual improvement above the test-retest variation (yes/no) as measured by a number of ETDRS letters will be summarized for study eye and the difference between eyes (study eye minus fellow eye) for all participants.

The 4-meter refraction (sphere, cylinder, and axis) observed values will be summarized for the study eye for all participants.

Summary statistics of all ETDRS visual acuity observed values and the change from baseline by study eye and the difference between eyes (study eye minus fellow eye) for all participants will be presented.

The difference between the study eye and the fellow eye of ETDRS letters, the difference at each visit, along with its change from baseline data, will be summarized. At each post-baseline visit, the change from baseline in the difference between the study eye and the fellow eye will be tested by a nonparametric Wilcoxon signed rank test as the primary method. The p-value from the t-test and the Shapiro-Wilk Normality test will also be provided.

All visual acuity data will be listed.

In-text displays:

- Average Plot of BCVA (ETDRS Letters) Change from Baseline Over Time
- Individual Plot of BCVA (ETDRS Letters) Change from Baseline Over Time

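### The responder proportion counts anyone ever improved at two consecutive visits; no planned output counts how many responders kept or lost the gain

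*SAP*

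**What the plan says.** SAP 3.5.1 defines the responder for each visual function test: "Participants who have a post baseline reading greater than the test-retest value for at least 2 consecutive assessments" are classed as improved. Protocol 5.9.3.2 has the same criterion, an improvement from baseline that exceeds test-retest variation and "is sustained for at least 2 consecutive assessments". The protocol then says how it is reported: "Measures will be reported individually and aggregated across participants as the proportion who satisfy the above criteria". SAP 3.5.2 carries this into the visual acuity output: "Achievement of visual improvement above the test-retest variation (yes/no) as measured by a number of ETDRS letters will be summarized", for the study eye and for the between-eye difference. Sections 3.5.3 and 3.5.4 do the same for contrast sensitivity and maximum reading speed.

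The visit schedule is given in SAP 3.5.2: "Visual acuity was assessed at the Month 9, 12, 18, 24, 36, 48, and 60 visits". The other two tests follow the same schedule.

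On purpose, Protocol 4.3 says that the schedule of assessments is "designed to evaluate for longer term durability and safety associated with the subretinal administration of the antecedent gene therapy", and the secondary objective in SAP 2.1.2 is to "explore the longer-term efficacy of" the two products.

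For each of the three tests, SAP 3.5.2 to 3.5.4 also plan summaries of change from baseline, a Wilcoxon signed rank test of the between-eye change at each post-baseline visit, average and individual plots over time, and listings.

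**The concern.** The rule names no visits, sets no condition at the end of follow-up and says nothing about later loss. A participant above threshold only at Months 9 and 12, and back at baseline at the five later visits, counts the same as one who keeps the gain to Month 60. The aggregated efficacy figure can be settled within the first year, while the later visits are what this follow-up study adds. A reader could easily take a proportion from a five-year study as the share of participants still improved at five years.

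There is also a wording problem in the rule itself. SAP 3.5.1 compares a *post baseline reading* with the test-retest value. Taken literally, that sets a raw score against a measure of variability, and it conflicts with the protocol criterion restated just above it, which is about improvement from baseline.

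**Working it through.** The documents state no expected responder rate, so there is no figure to reproduce. The check has two parts.

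**1. Counting, with no assumptions about the data**

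Input: seven visits (Months 9, 12, 18, 24, 36, 48, 60).

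- Consecutive pairs: 7 − 1 = 6, spanning 3, 6, 6, 12, 12 and 12 months. Only the Month 48–60 pair includes the last visit; the other five do not.
- Above/below patterns: 2^7 = 128. Patterns with no two adjacent visits above threshold number 34 (the sequence for 1 to 7 visits is 2, 3, 5, 8, 13, 21, 34). So 128 − 34 = 94 satisfy the rule.
- Qualifying patterns below threshold at Month 60: 2^6 − 21 = 43.
- Qualifying patterns not above threshold at both Months 48 and 60: 94 − 2^5 = 62.

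These counts show what the rule permits. They are not probabilities.

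**2. Simulation, illustrative only**

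Assumptions not in the documents: independent normal errors with equal SD in each eye, two or three baseline readings per eye, no missing visits, only the seven visits of this study counted, and the rule applied to the study eye's change from mean baseline. Where there is a gain, it is 4 SD. There were 200,000 participants per scenario.

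The threshold is 1.96 × SD, with three versions of the SD: the true value; the conventional pooled estimate, √[(SS1 + SS2)/(n1 + n2 − 2)]; and the SAP formula as printed, which multiplies each eye's sum of squares by (n − 1). With two readings n − 1 = 1, so the printed and pooled versions coincide. With three readings the printed variance is twice the pooled one.

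Each cell gives the percentage classed as responders by any consecutive pair / by Months 48 and 60 both above threshold.

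| Baseline readings | SD used | No true gain | Gain at Months 9 and 12 only | Gain kept to Month 60 |
|---|---|---|---|---|
| 2 | true | 3.9 / 0.9 | 91.1 / 0.9 | 99.6 / 91.1 |
| 2 | pooled (= printed) | 13.9 / 4.6 | 88.4 / 4.7 | 97.4 / 88.2 |
| 3 | true | 2.5 / 0.5 | 92.7 / 0.5 | 99.9 / 92.8 |
| 3 | pooled | 7.6 / 2.0 | 90.5 / 2.0 | 99.0 / 90.4 |
| 3 | printed | 3.0 / 0.7 | 73.2 / 0.7 | 91.7 / 73.3 |

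The any-pair rule gives 73% to 93% for a gain that is wholly lost after Month 12 and 92% to 99.9% for one that is kept. If all 34 dosed participants (23 + 11, SAP 2.2.3) had the transient profile, about 25 to 32 would be reported as responders. The late-visit rule gives 0.5% to 5% against 73% to 93%, so it separates the two cases.

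**The case against.** The strongest reply is that the SAP does not hide later loss. For all three analysed tests it plans individual plots of change over time, full listings, and by-visit summaries and tests through Month 60. With 23 and 11 participants dosed, individual plots are readable, and the protocol describes efficacy as assessed participant by participant and descriptively. This stands. A reader might infer that no planned analysis can show durability, and the documents do not support that. What is missing is a count. To obtain one, a reader would have to compare each plotted line with that participant's own test-retest value.

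Second, the SAP applies the protocol's definition faithfully. This also stands: the two-consecutive-assessment criterion is the protocol's secondary outcome, so there is no contradiction between the documents on it, and nothing is miscalculated. The durability statement sits in the protocol's risk section and describes the assessment schedule; nowhere is the responder proportion named as the measure of durability. The case for a supplementary summary rests on that design aim together with the longer-term efficacy objective.

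Third, a reader might infer that six chances to qualify produce a high false-responder rate. No single rate can be supported. The study-eye figure runs from about 3% to 14% depending on the number of baseline readings and the variance formula. Much of the upper end comes from estimating each participant's SD on two to four degrees of freedom. Allowing any of six pairs multiplies the rate roughly three to five times relative to the Month 48–60 pair alone. False positives are in any case a separate matter from durability.

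Fourth, the intended meaning of the rule is clear from context: the neighbouring text speaks of improvement from baseline. The wording correction is therefore minor, though still worth making in a sentence that will be programmed from.

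**Conclusion.** The point holds in limited form. The responder proportion is an ever-improved-twice-in-a-row measure that Months 9 and 12 can satisfy and later loss does not undo. It cannot by itself say how many participants kept a gain, and no other planned output counts them. That follows from the text and the pattern counts alone.

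The simulated percentages rest on the stated assumptions, above all independent errors and a 4 SD gain, and are illustrative. They show that the proportion barely separates a transient gain from a durable one. Any false-responder rates should be presented the same way: for the study eye, about 3% to 14% for any pair and about 0.5% to 4.6% for Months 48 and 60.

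This is a worthwhile and inexpensive addition to the SAP, not an error that invalidates a planned analysis.

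**What to change.** 1. Keep the protocol-defined responder and label it in the tables as an ever-responder.
2. For each analysed visual function test and each product, add the number and proportion whose change from baseline exceeds the test-retest value at both Month 48 and Month 60.
3. Add the number of ever-responders who later fell below the test-retest value.
4. Show participants with a missing Month 48 or Month 60 visit as their own category. Give the late-visit proportion both among those assessed and with missing counted as non-response, so that dropout is not read as lost effect.
5. In SAP 3.5.1, replace *post baseline reading* with *post-baseline change from baseline*.

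The cost is a few extra rows per responder table, with no new data and no change to a protocol endpoint. SAP section 1 says that the plan is finalised before database lock, so these changes belong before that point. The downsides are that the late-visit proportion can be no higher than the ever-responder proportion, and that its denominators are small, at most 23 and 11, so each participant shifts the result by about 4 percentage points (1/23) or 9 (1/11).

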#### **5.5.2 Secondary Outcomes**

The secondary outcomes are measures of the efficacy of the ATIMP; these will be performed on an individual participant basis and will be descriptive in nature:

- 1) Any improvements in visual function from baseline that are greater than the test-retest variation and are sustained for at least two consecutive assessments.
- 2) Any improvement in retinal function from baseline that is greater than test-retest variation and measurable by electrophysiology (pattern ERG, or full-field ERG).

3) Quality of life will be measured by the Impact of Visual Impairment (IVI) questionnaire and the EQ5D-5L.

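### SAP 3.5.1 prints a study-eye test-retest variance that is not a pooled variance; under any formula the 1.96·S threshold rests on one participant's few baseline readings and leaves out baseline-mean error

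*SAP*

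**What the plan says.** SAP 3.5.1 sets the test-retest threshold at 1.96 times the square root of S_p², "where S_p^2 is the within-participant variance for each participant and will be derived as" a printed formula. Write SS for an eye's sum of squared deviations from its own baseline mean. The study-eye formula is then [(n1−1)·SS1 + (n2−1)·SS2] / (n1+n2−2). For the study-eye-minus-fellow-eye difference, the same section uses SS/(n−1) with no multiplier, and puts n at 2 to 3.

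The thresholds are not new to this study: "The test-retest values from studies MGT006 and MGT012 will be used for the MGT007 final analyses". On the decision rule, "Participants who have a post baseline reading greater than the test-retest value for at least 2 consecutive assessments" are classed as improved on that test; the sentence before it speaks of improvement from baseline. For visual acuity, contrast sensitivity and reading speed (SAP 3.5.2 to 3.5.4), "The arithmetic mean of the multiple observations at baseline will be used as the baseline value". In SAP 3.5.2 the yes/no result "will be summarized for study eye and the difference between eyes (study eye minus fellow eye) for all participants".

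Protocol 5.5.2 says of the secondary outcomes that "these will be performed on an individual participant basis and will be descriptive in nature", and Protocol 5.9.3.2 aggregates them as the proportion of participants who meet the criteria. Neither document gives an error rate for the rule or a numerical test-retest value.

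**The concern.** There are two separate problems.

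- **The formula as printed.** Weights of (n−1) belong on sample variances. Here they sit on sums of squares, so the threshold depends on how many baseline readings a participant happened to have.
- **The calibration, whichever formula was meant.** What is judged is a follow-up value minus a mean of n baseline readings. The multiplier 1.96 assumes that the SD is known and allows nothing for error in the baseline mean.

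The rule carries weight. SAP section 4 drops full-field and pattern ERG from analysis, so the visual-function rule is the only protocol responder criterion left, and it is applied to three tests. Protocol 4.4 states that there is no comparator, so no control group shows the background rate of false improvers.

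**Working it through.** **Inputs**
- Multiplier 1.96, both variance formulas and the two-consecutive rule: SAP 3.5.1.
- Seven post-baseline visits (Months 9 to 60): SAP 3.5.2.
- 23 and 11 participants dosed, 34 in all: SAP 2.2.3.
- Readings per eye, 2 to 3: an assumption, because the SAP states this count only for the difference.
- Further assumptions: independent normal errors, equal SD σ in both eyes and at baseline and follow-up, no true change, and the rule read as change from baseline.

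The plan gives no figure to reproduce.

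**Step 1: the printed variance.** Since E[SS] = (n−1)σ², the printed form has expectation σ²·[(n1−1)² + (n2−1)²]/(n1+n2−2). The pooled form (SS1+SS2)/(n1+n2−2) has expectation σ².
- 2+2 readings: (1+1)/2 = 1.00, threshold ×1.00
- 2+3 readings: (1+4)/3 = 1.67, threshold ×1.29
- 3+3 readings: (4+4)/4 = 2.00, threshold ×1.41

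Example with left eye 40/42/44 and right eye 41/43/45 letters: SS = 8 in each eye. Printed S² = (2·8 + 2·8)/4 = 8, threshold 1.96·√8 = 5.54 letters. Pooled S² = 16/4 = 4, threshold 3.92 letters.

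**Step 2: one visit.** The change has SD σ·√(1+1/n), so the false-crossing probability is P(t_df > 1.96·k/√(1+1/n)). Here k = √(n−1) for the printed study-eye form and 1 otherwise. The df are 2n−2 for the study eye and n−1 for the difference.
- Study eye, 2+2: P(t₂ > 1.600) = 12.5%
- Study eye, 3+3 printed: P(t₄ > 2.400) = 3.7%
- Study eye, 3+3 corrected: P(t₄ > 1.697) = 8.2%
- Difference, n=2: P(t₁ > 1.600) = 17.8%
- Difference, n=3: P(t₂ > 1.697) = 11.6%

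**Step 3: sustained at two consecutive visits.** Simulation and numerical integration over the baseline-mean error and the chi-square distribution of S agree:

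| Case | 7 visits | 5 visits | 3 visits |
|---|---|---|---|
| Study eye 2+2 | 13.9% | 10.9% | 6.8% |
| Study eye 3+3, printed | 3.0% | 2.2% | 1.3% |
| Study eye 3+3, corrected | 7.6% | 5.6% | 3.3% |
| Difference, n=2 | 21.2% | 17.2% | 11.3% |
| Difference, n=3 | 12.4% | 9.5% | 5.8% |

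With two readings in one eye and three in the other, the seven-visit study-eye rate is 5.6 to 6.7% as printed and 9.3 to 10.8% corrected. With σ known and an error-free baseline mean it would be about 0.4%.

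**Step 4: expected counts.** If all 34 enrol, attend seven visits and share one reading count, the expected false improvers per test are 34 × 0.1386 = 4.7 (2+2), 34 × 0.0299 = 1.0 (3+3 printed) or 34 × 0.0761 = 2.6 (3+3 corrected).

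**Step 5: unequal variance.** If follow-up variance is 1.5 to 2 times baseline variance, the seven-visit study-eye rates become 16.6 to 19.0%, 4.4 to 5.9% and 10.4 to 13.0% in the same order. The rates in Step 3 are therefore not upper bounds.

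**The case against.** The symbol S_p², the (n−1) weights and the denominator are those of the standard pooled variance Σ(n−1)s², so the printed form may be a notation slip. A divisor could also have been lost in the machine reading of the PDF. Because the values are imported, no wrong calculation in this study has been shown. This stands, and it is why the first step is a check against the parent programs. It does not touch the calibration point.

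The SAP promises no error rate, the outcomes are individual and descriptive, and 1.96·S is offered as test-retest variation rather than as a prediction limit. That is fair on status. Even so, the threshold is applied to a change, and it understates how much a change varies unless the printed factor happens to compensate. It does so at 3+3: the printed threshold is about 2.77σ (1.96·√2), above the 2.26σ (1.96·√(4/3)) that baseline-mean error alone would require. The rule is not materially lax in that case.

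Reading counts are unknown. With four readings per eye the rates would be 0.6% (printed) or 5.0% (corrected), outside the cases tabulated. This limits confidence in the size of the problem, but it also confirms that the rate depends on the count.

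The wording about a post-baseline reading is largely settled by its context. Observed values, changes, individual plots and listings are planned alongside the responder summary.

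**Conclusion.** The concern holds. As printed, the study-eye variance is not a pooled variance and does not match the between-eye formula beside it; this matters only when an eye has more than two readings. Whichever formula was used, S rests on 2 to 4 df for the study eye (if each eye has 2 to 3 readings) and 1 to 2 df for the difference, and neither formula has a term for baseline-mean error.

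For the study eye, which is the protocol's criterion, the false sustained-improvement rate over seven visits runs from 3.0% to 13.9% according to reading count and programmed formula, under the assumptions listed. The between-eye responder summary is an addition by the SAP; its rates are higher, but it also has its own change summaries and tests. The exposure is a responder proportion that cannot be interpreted without knowing the reading counts and the formula. The primary safety conclusion is not affected.

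**What to change.** 1. Correct the study-eye variance to (SS1+SS2)/(n1+n2−2). Check it against the MGT006 and MGT012 programs, and recompute from parent baseline data if the printed form was used.
2. State that the change from baseline must exceed the threshold at two consecutive assessments.
3. Step 1 alone loosens the rule at 3+3 (3.0% to 7.6%). So keep the planned per-participant classification and report beside it, as a sensitivity analysis, the responder proportion from an SD pooled across participants within each product: S_w² = total SS / total df, with threshold t(0.975, pooled df)·S_w·√(1+1/n_i). Do this for the study eye and for the difference.
4. Show the number of baseline readings per participant in both tables, and footnote the difference table with its 1 to 2 df.

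The work is SAP wording, a program check and one extra table from data already held.

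The pooled rule has costs that the SAP should state. With a common SD, its seven-visit false rate is 1.1 to 1.5% (study eye) or 1.1 to 1.6% (difference), but it is usually less sensitive. For a true gain of 2 within-eye SD over seven visits, detection changes as follows:

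| Case | Planned rule | Pooled rule |
|---|---|---|
| Study eye, n=2 | 70% | 44 to 46% |
| Study eye, n=3 | 43% printed, 69% corrected | 52 to 53% |
| Difference, n=2 | 59% | 21 to 23% |
| Difference, n=3 | 53% | 25 to 26% |

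It also assumes one within-person SD across adults and children. If SDs vary (assumed log-SD 0.5), about 8 to 9% of the noisiest quarter would be false improvers, against under 0.1% of the steadiest; the per-participant rule's rate does not vary with SD. Classifications may differ from those in the parent studies. For these reasons the pooled rule belongs beside the planned rule and not in its place.
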